9.2.2. Method of Detecting AEs and SAEs

Care will be taken not to introduce bias when detecting AE and/or SAE. Open-ended and non-leading verbal questioning of the participant is the preferred method to inquire about AE occurrence.

9.2.3. Follow-up of AEs and SAEs

After the initial AE/SAE report, the investigator is required to proactively follow each participant at subsequent visits/contacts. All SAEs will be followed until the event is resolved, stabilized, otherwise explained, or the participant is lost to follow-up (as

defined in Section 8.3). Further information on follow-up procedures is given in [Appendix 4](#).

9.2.4. Regulatory Reporting Requirements for SAEs

- Prompt notification by the investigator to the sponsor of a SAE is essential so that legal obligations and ethical responsibilities towards the safety of participants and the safety of a study treatment under clinical investigation are met.
- The sponsor has a legal responsibility to notify both the local regulatory authority and other regulatory agencies about the safety of a study treatment under clinical investigation. The sponsor will comply with country-specific regulatory requirements relating to safety reporting to the regulatory authority, Institutional Review Boards (IRB)/Independent Ethics Committees (IEC), and investigators.
- Investigator safety reports must be prepared for SUSARs according to local regulatory requirements and sponsor policy and forwarded to investigators as necessary.
- An investigator who receives an investigator safety report describing a SAE or other specific safety information (eg, summary or listing of SAE) from the sponsor will review and then file it along with the Investigator's Brochure and will notify the IRB/IEC, if appropriate according to local requirements.
- Further details can be found in [Appendix 7](#).

9.2.5. Pregnancy

- Details of all pregnancies in female participants and, female partners of male participants will be collected after the start of study treatment and until 30 days after the last dose.
- If a pregnancy is reported, the investigator should inform GSK within 24 hours of learning of the pregnancy and should follow the procedures outlined in [Appendix 5](#).
- Abnormal pregnancy outcomes (eg, spontaneous abortion, fetal death, stillbirth, congenital anomalies, ectopic pregnancy) are considered SAE.

9.3. Treatment of Overdose

For this study, any dose of GSK2982772 greater than that intended in this study will be considered an overdose.

There is no specific antidote for overdose with GSK2982772.

In the event of an overdose, the investigator should:

1. Contact the Medical Monitor immediately.

2. Closely monitor the participant for AE/SAE and laboratory abnormalities until study treatment can no longer be detected systemically (at least 48 hours following the last dose of GSK2982772).
3. Obtain a plasma sample for PK analysis if requested by the Medical Monitor (determined on a case-by-case basis).
4. Document the quantity of the excess dose as well as the duration of the overdosing in the CRF.

Decisions regarding dose interruptions or modifications will be made by the investigator in consultation with the Medical Monitor based on the clinical evaluation of the participant.

9.4. Safety Assessments

Planned time points for all safety assessments are provided in the SoA.

9.4.1. Physical Examinations

- A complete physical examination will include, at a minimum, assessments of the skin, cardiovascular, respiratory, GI and neurological systems. Height and weight will also be measured and recorded.
- A brief physical examination will include, at a minimum, assessments of the skin, lungs, cardiovascular system, and abdomen (liver and spleen).
- Investigators should pay special attention to clinical signs related to previous serious illnesses.

9.4.2. Vital Signs

- Vital signs will be measured in a semi-supine position after 5 minutes rest and will include temperature, systolic and diastolic blood pressure, heart rate and respiratory rate.
- The acceptable deviations from the nominal vital signs measurement time points are:
 - The pre-dose vital signs measurements will be taken ≤ 2 hours before dosing.
 - Post-dose vital signs measurements will be taken ± 15 minutes from the nominal post-dose time points.
 - Discharge vital signs measurements will be taken ± 1 hour from the nominal time point.
- If a participant shows an abnormal assessment at any stage, repeat measurements may be made and the abnormality followed to resolution if required. Additional measurements may be taken as deemed necessary by the investigator.
- Any clinically significant abnormality, including changes from baseline (pre-dose Day 1), must be reported as an AE.

9.4.3. Electrocardiograms

- Triplicate 12-lead ECGs will be obtained at screening and single 12-lead ECGs will be obtained as outlined in the SoA using an ECG machine that automatically calculates the heart rate and measures PR, QRS, QT, and QTc intervals. If a single ECG shows a QTc increase of ≥ 60 msec from baseline (pre-dose Day 1), two further ECGs should be performed over a brief period (e.g. 5 to 10 minutes) and the assessment made on the mean QTc of the triplicate ECGs. Refer to Section 8.1.2 for QTc withdrawal criteria and additional QTc readings that may be necessary.
- The QTc should be based on averaged QTc values of triplicate ECGs obtained over a brief (e.g. 5 to 10 minutes) recording period.
- The acceptable deviations from the nominal ECG measurement time points are:
 - The pre-dose ECG measurements will be taken ≤ 2 hours before dosing
 - Post-dose ECG measurements will be taken ± 15 minutes from the nominal post-dose time point.
 - Discharge ECG measurements will be taken ± 1 hour from the nominal time point.
- ECGs are to be measured after participant has been in a semi-supine or supine position after approximately 5 minutes rest.
- If a participant shows an abnormal assessment at any stage, repeat measurements may be made and the abnormality followed to resolution if required. Additional measurements may be taken as deemed necessary by the investigator.
- Any clinically significant abnormality, including changes from baseline (pre-dose Day 1), will be reported as an AE.

9.4.4. Clinical Safety Laboratory Assessments

- Refer to [Appendix 2](#) for the list of clinical laboratory tests to be performed and to the SoA for the timing and frequency.
- Blood samples for scheduled laboratory assessments will be taken following an overnight fast.
- The acceptable deviations from the nominal blood sampling time points for laboratory assessments are:
 - The pre-dose blood sample will be taken ≤ 2 hours before dosing
 - Post-dose blood samples will be taken ± 1 hour from the nominal blood sampling time except when the time point coincides with the PK blood sampling time. In this situation, the time window for the PK sample applies.
- The acceptable deviations from the nominal urine sampling time points for urinalysis are:
 - The pre-dose urine sample will be taken ≤ 3 hours before dosing or the first void of the day

- Post-dose urine samples will be taken \pm 2 hour from the nominal urine sampling time.
- The investigator must review the laboratory report, document this review, and record any clinically relevant changes occurring during the study in the AE section of the CRF. The laboratory reports must be filed with the source documents. Clinically significant abnormal laboratory findings are those which are not associated with the underlying disease, unless judged by the investigator to be more severe than expected for the participant's condition.
- All laboratory tests with values considered clinically significantly abnormal during participation in the study or within 7 days after the last dose of study treatment should be repeated until the values return to normal or baseline or are no longer considered significantly abnormal by the investigator or medical monitor.
- If such values do not return to normal/baseline within a period of time judged reasonable by the investigator, the etiology should be identified and the sponsor notified.
- All protocol-required laboratory assessments, as defined in [Appendix 2](#), must be conducted in accordance with the laboratory manual and the SoA.
- If laboratory values from non-protocol specified laboratory assessments performed at the institution's local laboratory require a change in participant management or are considered clinically significant by the investigator (eg, SAE or AE or dose modification), then the results must be recorded in the CRF.

9.4.5. Suicidal Risk Monitoring

GSK2982772 is considered to be a CNS-active drug. There has been some concern that some CNS-active drugs may be associated with an increased risk of suicidal thinking or behaviour when given to some patients with disease. Although this drug has not been shown to be associated with an increased risk of suicidal thinking or behaviour when given to healthy volunteers, GSK considers it important to monitor for such events before or during clinical studies with compounds such as this.

Participants being treated with GSK2982772 should be monitored appropriately for suicidal ideation and behaviour or any other unusual changes in behaviour. Study medication must be immediately discontinued in all participants who experience signs of suicidal ideation or behaviour.

Families and caregivers of patients being treated with GSK2982772 should be alerted about the need to monitor participants for the emergence of unusual changes in behaviour, as well as the emergence of suicidal ideation and behaviour and to report such symptoms immediately to the study Investigator.

At Screening, the 'Baseline/Screening C-SSRS' will be completed in Part B only. Assessments done at pre-dose Day 1 and Day 4, the 'Since Last Visit C-SSRS' will be completed in Part B only. GSK Version 4.1 of both rating scales will be used.

Participants who answer 'yes' to any suicidal behaviour or 'yes' to suicidal ideation Questions 4 or 5 will be referred to their General Practitioner or appropriate psychiatric care and be discontinued from study medication. The Medical Monitor will be notified. If appropriate, an AE or SAE should be reported (see Section 9.2). In addition, the Investigator should complete a Possible Suicidality Related Adverse Event (PSRAE) form to collect detailed information on the circumstances of the reported AEs which, in the Investigator's opinion, are possibly suicidality-related. These may include, but are not limited to, an event involving suicidal ideation, a preparatory act toward imminent suicidal behaviour, a suicide attempt, or a completed suicide.

9.5. Pharmacokinetics

- Blood samples of approximately 2 mL will be collected for measurement of plasma concentrations of GSK2982772 as specified in the SoA (see Section 2). Instructions for the collection and handling of biological samples will be provided by the sponsor. The actual date and time (24-hour clock time) of each sample will be recorded.
- Processing, storage and shipping procedures are provided in the Study Reference Manual (SRM) or equivalent.
- The acceptable deviations from the nominal post-dose blood sampling times are as follows:
 - The pre-dose blood sample will be taken ≤ 1 hour before dosing.
 - Post-dose samples will be taken within ± 10 minutes of the nominal post-dose sampling time
- Samples will be used to evaluate the PK of GSK2982772. Samples collected for analyses of GSK2982772 plasma concentration may also be used to evaluate safety aspects related to concerns arising during or after the study.
- Genetic analyses will not be performed on these plasma samples. Participant confidentiality will be maintained.

Plasma analysis will be performed under the control of Platform Technology & Science (PTS), In Vitro/In Vivo Translation (IVIVT) and Third Party Resourcing (TPR), GSK. Concentrations of GSK2982772 will be determined in plasma using the current approved bioanalytical methodology. Raw data will be archived at the Bioanalytical site as detailed in the SRM or equivalent.

9.6. Pharmacodynamics

Pharmacodynamic parameters are not evaluated in this study.

9.7. Genetics

Genetics are not evaluated in this study.

9.8. Biomarkers

Biomarkers are not evaluated in this study.

9.9. Health Economics OR Medical Resource Utilization and Health Economics

Health Economics/Medical Resource Utilization and Health Economics parameters are not evaluated in this study.

10. STATISTICAL CONSIDERATIONS

10.1. Hypotheses

No formal hypothesis will be tested. However, point estimates and corresponding 90% confidence intervals will be derived for C_{max} , $AUC_{(0-inf)}$, C_{12} and C_{24} and peak to trough concentration ratio for each test minitab MR formulation in a capsule (120 mg) relative to the IR formulation (120 mg).

10.2. Sample Size Determination

10.2.1. Sample Size Determination - Part A

To date, there are no MR formulation variability data available. The maximum between-subject coefficient of variation (CV_b) for the PK parameters observed in Study 200975 following GSK2982772 capsule formulation were used for precision estimates; CV_b (%) for $AUC_{(0-inf)}$ and C_{max} for 120 mg GSK2982772 IR capsule formulation were 29.0 and 31.5 respectively. Therefore, the estimates of within subject coefficient of variation (CV_w [%]) are 20.3% and 18.8% for $AUC_{(0-inf)}$ and C_{max} , respectively. Based on these estimates of variability and a sample size of 12 completers, it is estimated that the lower and upper bounds of the 90% confidence interval (CI) for the geometric mean ratio (MR/IR) of AUC and C_{max} will be within approximately 15.3% and 14.2% of the point estimate respectively.

Since it is expected that the MR formulation is to reduce the C_{max} by 50% whilst maintaining the AUC, a sample size of 12 ensures that the 90% CI is within the region 0.8-1.25 for AUC and 0.4-0.625 for C_{max} , if the observed geometric ratio is 0.93-1.08 for AUC and 0.47-0.54 for C_{max} .

Sample Size Sensitivity – Part A

Using estimates of parameter (this can be any PK parameter AUC, C_{max}) variability observed in Study 200975, the precision of these estimates calculated as half width of a 90% confidence interval for the mean ratio (MR/IR) and expressed as distance from mean to limits for 10, 12, 14 and 16 participants has been calculated ([Table 5](#)).

Table 5 Precision Estimate of Mean – Part A

CV _w (%)	Precision of Mean (%)			
	N=10	N=12	N=14	N=16
15	12.70	11.30	10.30	9.50
18.8	16.00	14.20	12.90	11.90
20	17.30	15.30	13.90	12.90

For example, based upon the estimate of variability (CV_w%) of 20 and a sample size of 14, it is estimated that the lower and upper bounds of the 90% confidence interval for the means of the PK parameter (eg, AUC, C_{max}) will be within approximately 13.9% of the point estimate.

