10.2.2. Sample Size Determination - Part B

No repeat dose MR formulation variability data are currently available. Therefore, the maximum CV_b for the PK parameters were observed in the study 200972 following repeat dose of GSK2982772 capsule formulation; CV_b (%) for AUC_(0-τ) and C_{max} for 20mg QD GSK2982772 IR capsule formulation on Day 1 is 36.1 and 27.1 respectively. Therefore, the estimates of equivalent CV_w (%) are 23.2 and 17.6 for C_{max} and AUC_(0-τ) respectively. Based on these estimates of variability and a sample size of 8 completers, it is estimated that the lower and upper bounds of the 90% confidence interval for the means of AUC_(0-τ) and C_{max} will be within approximately 12.1% and 16.7% of the point estimate respectively.

Sample Size Sensitivity – Part B

Using estimates of parameter (this can be any PK parameter AUC, C_{max}) variability, the precision of these estimates calculated as half width of a 90% confidence interval for the mean and expressed as distance from mean to limits for 4, 6, 8 and 10 participants has been calculated (Table 6).

Table 6 Precision Estimate of Mean – Part B

CV _b (%)	Precision of Mean (%)			
	N=4	N=6	N=8	N=10
18.4%	23.6	16.0	12.8	11.0
19.3%	25.1	16.9	13.6	11.6
24.4%	32.6	21.8	17.4	14.9
25.5%	34.2	22.8	18.2	15.6

For example, based upon the estimate of variability ($CV_b\%$) of 19.3 and a sample size of 4, it is estimated that the lower and upper bounds of the 90% confidence interval for the means of the PK parameter (eg, AUC, C_{max}) will be within approximately 25.1% of the point estimate.

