10.2.3. Sample Size Determination - Part C

The maximum between-subject coefficient of variation (CV_b) for the PK parameters observed in Part A of Study 205017 were used for precision estimates; CV_b (%) for $AUC_{(0-inf)}$ and C_{max} were 48.7% and 58.5%, respectively. Therefore, the estimates of within-subject coefficient of variation (CV_w [%]) are 30.9% and 36.7% for $AUC_{(0-inf)}$ and C_{max} , respectively. Based on these estimates of variability and a sample size of 12 completers, it is estimated that the lower and upper bounds of the 90% CI for the geometric mean ratio (MR/IR) of AUC and C_{max} will be within approximately 24.3% and 29.2% of the point estimate, respectively.

Since it is expected that the MR tablet formulation is to reduce the C_{max} by 50% whilst maintaining the AUC, a sample size of 12 ensures that the 90% CI is within the region 0.748-1.342 for AUC and 0.364-0.698 for C_{max} , if the observed geometric ratio is 0.93-1.08 for AUC and 0.47-0.54 for C_{max} .

Sample Size Sensitivity – Part C

Using estimates of parameter (this can be any PK parameter AUC, C_{max}) variability observed in Part A of Study 205017, the precision of these estimates calculated as half width of a 90% CI for the mean ratio (MR/IR) and expressed as distance from mean to limits for 10, 12, 14 and 16 participants has been calculated (Table 7).

Table 7 Precision Estimate of Mean – Part C

CV _w (%)	Precision of Mean (%)			
	N=10	N=12	N=14	N=16
30.9	27.5	24.3	22.0	20.3
36.7	33.1	29.2	26.4	24.3

For example, based upon the estimate of variability ($CV_w\%$) of 30.9 and a sample size of 14, it is estimated that the lower and upper bounds of the 90% CI for the means of the PK parameter (eg, AUC, C_{max}) will be within approximately 22.0% of the point estimate.

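### Protocol 10.2.1 and 10.2.2 contradict themselves on which of AUC and Cmax is the more variable, and the stated precisions for Parts A and B carry the mismatch

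*Protocol*

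**What the plan says.** Each part takes between-subject CVs (CVb), converts them to within-subject CVs (CVw) and derives a 90% CI precision. No section states the conversion rule.

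- **Part A (Protocol 10.2.1).** The CVb values for AUC(0-inf) and Cmax with the 120 mg "IR capsule formulation were 29.0 and 31.5 respectively". The CVw values "are 20.3% and 18.8% for" AUC(0-inf) and Cmax. With "a sample size of 12 completers", the interval limits for AUC and Cmax "will be within approximately 15.3% and 14.2% of the point estimate respectively". Precision there is "calculated as half width of a 90% confidence interval for the mean ratio (MR/IR").
- **Part B (Protocol 10.2.2).** CVb for AUC(0-τ) and Cmax with the 20 mg "IR capsule formulation on Day 1 is 36.1 and 27.1 respectively". The CVw values "are 23.2 and 17.6 for" Cmax and AUC(0-τ), with the two parameters named in the opposite order from the sentence before. With 8 completers, precision is given as 12.1% (AUC) and 16.7% (Cmax).
- **Part C (Protocol 10.2.3).** CVb is 48.7% (AUC) and 58.5% (Cmax). The CVw values "are 30.9% and 36.7% for" AUC and Cmax.

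**The concern.** In Part A, AUC has the smaller CVb but the larger CVw. In Part B, AUC has the larger CVb but the smaller CVw. Part C keeps the order. No single increasing conversion can reverse the ranking, yet each section presents its CVw values as following from its CVb values. Somewhere in each of 10.2.1 and 10.2.2 the AUC and Cmax labels have been exchanged.

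At stake is the accuracy of the planning figures. If the CVb values are right as printed, each precision in Parts A and B belongs to the other parameter, and Part A Cmax and Part B AUC are stated more favourably than the inputs support. Anyone who takes these CVs into a later study inherits the error.

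**Working it through.** **Inputs.** All CVs, sample sizes (12 and 8) and precisions come from Protocol 10.2.1 to 10.2.3. The conversion rule is inferred, not quoted.

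**Step 1: infer the rule from Part C.** On the log scale the variance is ln(1 + CV²).
- AUC: ln(1 + 0.309²) / ln(1 + 0.487²) = 0.0912 / 0.2128 = 0.429.
- Cmax: ln(1 + 0.367²) / ln(1 + 0.585²) = 0.1264 / 0.2943 = 0.429.

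Both equal 3/7 to rounding, so the implied rule is CVw = √[(1 + CVb²)^(3/7) − 1].

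**Step 2: apply it to every printed CVb.**

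| Part, parameter | CVb printed | CVw by rule | CVw printed for that parameter |
|---|---|---|---|
| A, AUC | 29.0 | 18.8 | 20.3 |
| A, Cmax | 31.5 | 20.3 | 18.8 |
| B, AUC | 36.1 | 23.2 | 17.6 |
| B, Cmax | 27.1 | 17.6 | 23.2 |
| C, AUC | 48.7 | 30.9 | 30.9 |
| C, Cmax | 58.5 | 36.7 | 36.7 |

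All six printed CVw values appear to one decimal. In Parts A and B each sits against the other parameter.

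**Step 3: log-variance ratios, AUC then Cmax.**
- As labelled: Part A 0.50 and 0.37; Part B 0.25 and 0.74.
- With labels exchanged: Part A 0.430 and 0.427; Part B 0.428 and 0.431.

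Exchanging the labels brings all four into line with Part C.

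**Step 4: the precisions follow the attached CVw.**
- Part A, ratio of means, N = 12: exp{t × √ln(1 + CVw²) × √(2/12)} − 1. CVw 20.3% gives 15.9% (t on 11 df) or 15.1% (22 df), against 15.3% printed. CVw 18.8% gives 14.6% or 14.0%, against 14.2% printed.
- Part B, single mean, N = 8: exp{t × √ln(1 + CVw²) / √8} − 1 with 7 df. CVw 17.6% gives 12.4%, against 12.1% printed. CVw 23.2% gives 16.6%, against 16.7% printed.

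The agreement is approximate, because the degrees of freedom used are not given, but the pairing is clear. Table 5 also shows 14.2% against CVw 18.8% at N = 12. It shows 15.3% against CVw 20%, not 20.3%, which is a separate rounding matter.

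**Step 5: Part A target regions with the precisions exchanged** (AUC 14.2%, Cmax 15.3%).
- AUC: 0.93 / 1.142 = 0.814 and 1.08 × 1.142 = 1.233, inside 0.8 to 1.25.
- Cmax: 0.47 / 1.153 = 0.408 and 0.54 × 1.153 = 0.623, inside 0.4 to 0.625.

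**The case against.** **Which labels are wrong.** A reader might infer that the CVw labels must be the transposed ones, so that the Part B AUC precision of 12.1% is simply an error for 16.7%. The documents do not settle this. Cmax has the larger CVb in Parts A and C; only Part B has AUC larger. Part B also reorders its CVw sentence explicitly, and its precision sentence carries that assignment through consistently. If the Part B CVb labels are the ones reversed, 12.1% and 16.7% are correct as printed, and exchanging them would introduce an error. This is not proof, because study and dose differ between parts, but the objection stands: the direction needs the source values.

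**Whether a target region is breached.** A reader might also infer that, once exchanged, the Cmax interval escapes its upper bound of 0.625. With t on 11 df and CVw 20.3%, 0.54 × 1.159 = 0.626. But the protocol's printed 15.3% gives 0.623. The planned model has three observations per participant (SAP 8.1.5.1), about 22 df with 12 completers, and gives 0.54 × 1.151 = 0.622. The multipliers implied by Tables 5 and 7 at N = 12 (1.745 to 1.765) give 15.4% to 15.6%, hence 0.623 to 0.624. The same t on 11 df puts AUC as now labelled at 1.08 × 1.159 = 1.251, just over 1.25, so the exchange is not the cause. This reading fails.

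**Practical weight.** No formal hypothesis is tested (Protocol 10.1), Parts A and B were complete when Part C was added (Protocol 3.1), and reported intervals will come from observed data. All of that is correct. It limits the consequence to the planning record and its reuse; it does not remove the contradiction.

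**Conclusion.** Protocol 10.2.1 and 10.2.2 are each internally inconsistent, and the mismatch runs through to the stated precisions. That much rests on the printed figures alone: the rankings reverse, and one rule fits all six values only with the labels exchanged in Parts A and B. The 3/7 rule itself is an inference from Part C.

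The size is conditional. If the printed CVb values are right, one precision in each part is too favourable: Part A Cmax by 15.3 − 14.2 = 1.1 points, and Part B AUC by 16.7 − 12.1 = 4.6 points. If the CVb labels are the transposed ones, the printed CVw and precision figures stand. The sample sizes, the Part A regions of 0.8 to 1.25 and 0.4 to 0.625, and Part C are unaffected either way.

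**What to change.** Check the CVb values for AUC and Cmax against the source study cited in each section, separately for Parts A and B. Then, for each part:

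- **If the printed CVb values are confirmed.** Restate Part A as CVw 18.8% (AUC) and 20.3% (Cmax), with precision about 14.2% (AUC) and 15.3% (Cmax). Restate Part B as CVw 23.2% (AUC) and 17.6% (Cmax), with precision about 16.7% (AUC) and 12.1% (Cmax).
- **If the CVb labels are the transposed ones.** Exchange those labels and leave the CVw and precision figures as printed.

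Stating the CVb-to-CVw conversion rule in the text would let a reader verify the result. The Part A Cmax range does not need recalculating. The cost is one look-up and a wording change; if the CVb values are confirmed, one stated precision in each part becomes less favourable.

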#### 8.1.5.1. Statistical Methodology Specification

The following pharmacokinetic statistical analyses will only be performed if sufficient data is available (i.e. if participants have well defined plasma profiles).

Endpoint (log scale)

 
• AUC(0-inf)
 
• AUC(0-t) if AUC(0-inf) cannot be derived
 
• AUC(0-12) if BID
 
• AUC(0-24h)
 

 
• <math>C_{\max}</math>
 
• <math>C_{12h}</math> if BID
 
• <math>C_{24h}</math>
 

Model Specification

 
• For each endpoint a mixed model will be fit with 3 observations per participant expected in Part A, and 2 observations per participant in Part C. The model will contain formulation as a fixed, categorical effect, and a random intercept for subject.
 
• The Kenward and Roger method for approximating the denominator degrees of freedom and correcting for bias in the estimated variance-covariance of the fixed effects will be used.
 

Model Checking & Diagnostics

 
• Model assumptions will be applied, but appropriate adjustments may be made based on the data.
 
• In the event the model fails to converge, the RANDOM statement will be removed and alternative covariance structures such as CS, CSH, or UN for the R matrix will be used by specifying 'type=' on the REPEATED line. Akaike's Information Criteria (AIC) will be used to assist with the selection of covariance structure.
 
• Distributional assumptions underlying the model used for analysis will be examined by obtaining a normal probability plot of the residuals and a plot of the residuals versus the fitted values (i.e. checking the normality assumption and constant variance assumption of the model respectively) to gain confidence that the model assumptions are reasonable.
 
• If there are any departures from the distributional assumptions, alternative models will be explored using appropriate transformed data.
 
• If outliers are detected, an additional table will be produced with outlying observations omitted.
 

Model Results Presentation

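### Protocol 10.2.1 presents the Part A confidence intervals as certain to lie within set regions; at the limits of its observed-ratio ranges the probability is about 64–71% (AUC) and 81–95% (Cmax)

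*Protocol*

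**What the plan says.** Protocol Section 10.1 tests no formal hypothesis; instead "point estimates and corresponding 90% confidence intervals will be derived". Section 10.2.1 takes a within-subject CV of 20.3% for AUC and 18.8% for Cmax. "Based on these estimates of variability and a sample size of 12 completers", it estimates that the limits of the 90% CI for the MR/IR ratio "will be within approximately 15.3% and 14.2% of the point estimate respectively".

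The next paragraph goes further. It states that "a sample size of 12 ensures that the 90% CI is within the region" 0.8–1.25 (AUC) and 0.4–0.625 (Cmax), on one condition: that the observed ratio is 0.93–1.08 (AUC) or 0.47–0.54 (Cmax). It attaches no condition on the observed variability and gives no probability. Section 10.2.3 repeats the construction for Part C, with regions 0.748–1.342 and 0.364–0.698 and the same observed-ratio ranges.

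For the analysis, SAP Section 8.1.5.1 says that "a mixed model will be fit with 3 observations per participant expected in Part A" and 2 in Part C, with a random subject intercept and Kenward-Roger degrees of freedom.

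**The concern.** The width of a t-based confidence interval depends on the residual SD estimated from the trial's own data. A given observed ratio therefore does not fix where the interval ends. The protocol's sentence takes the planned half-width, which the preceding sentence properly calls approximate, and treats it as certain.

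Sections 10.2.1 and 10.2.3 are where the protocol supports 12 completers for its primary MR/IR comparisons. A reader would take an observed AUC ratio of 1.08 to guarantee an interval inside 0.8–1.25. What is at stake is whether that statement describes a property the design has.

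**Working it through.** **Inputs.** n = 12 and CVw 20.3% (AUC) and 18.8% (Cmax), from Protocol 10.2.1. Regions and observed-ratio ranges as above. Three observations per participant in Part A (SAP 8.1.5.1), so the residual df with complete data are about 2 × (12 − 1) = 22. A paired analysis of two formulations would have 11. The true CVw is taken to equal the planning value.

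**Step 1: the protocol's precision.** σ = √ln(1 + CVw²) = 0.2010 (AUC) and 0.1864 (Cmax). The half-width is exp(t₀.₉₅,df × σ × √(2/12)) − 1.
- 22 df (t = 1.717): 15.1% and 14.0%.
- 11 df (t = 1.796): 15.9% and 14.6%.

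The printed 15.3% and 14.2% lie between these, so they are reproduced closely.

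**Step 2: the sentence with the half-width held fixed.** 0.93/1.153 = 0.807 and 1.08 × 1.153 = 1.245; 0.47/1.142 = 0.412 and 0.54 × 1.142 = 0.617. All four lie inside the regions. With a fixed half-width, the protocol's arithmetic is correct.

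**Step 3: the sentence with the SD estimated.** At observed ratio g and region (L, U), the interval is inside if s ≤ s_max = min{ln(g/L), ln(U/g)} / (t × √(2/12)). The probability is P(χ²_df ≤ df × s_max²/σ²).

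Example, AUC at 1.08 with 22 df: the margin is ln(1.25/1.08) = 0.1462, and s_max = 0.1462/(1.717 × 0.4082) = 0.2085, against σ = 0.2010. Then 22 × (0.2085/0.2010)² ≈ 23.7, and P(χ²₂₂ ≤ 23.7) = 63.6%.

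| Observed ratio | Margin (log) | s_max, 22 df | Probability, 22 df | Probability, 11 df |
|---|---|---|---|---|
| AUC 0.93 | 0.1506 | 0.2148 | 70.9% | 59.7% |
| AUC 1.08 | 0.1462 | 0.2085 | 63.6% | 54.2% |
| AUC 1.00 | 0.2231 | 0.3183 | >99% | >99% |
| Cmax 0.47 | 0.1613 | 0.2300 | 94.5% | 83.2% |
| Cmax 0.54 | 0.1462 | 0.2085 | 80.9% | 67.9% |

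**Step 4: observed ratios with at least 90% probability, 22 df.** The 90th percentile of χ²₂₂/22 is 1.4006. The half-width at that SD is exp(1.717 × σ × √1.4006 × 0.4082) − 1 = 18.1% (AUC) and 16.7% (Cmax).
- AUC: 0.8 × 1.181 = 0.945 to 1.25/1.181 = 1.058.
- Cmax: 0.4 × 1.167 = 0.467 to 0.625/1.167 = 0.535.

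To two decimals the AUC range is about 0.95–1.06. The third decimal matters slightly at the top: at exactly 1.06 the margin is 0.1649, s_max is 0.2352 and the probability is 88%.

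**Step 5: Part C.** 0.93/1.243 = 0.748, 1.08 × 1.243 = 1.342, 0.47/1.292 = 0.364 and 0.54 × 1.292 = 0.698. The printed regions are the ratio limits widened by the planned half-widths. With CVw 30.9% and 36.7% and 11 df (two observations per participant), the probability at the limits is 52.6% and 52.1% (AUC) and 52.1% and 52.8% (Cmax).

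**Sensitivity.** The two Part A CVw values may be transposed. The ratio of within- to between-subject log-variance is 0.50 (AUC) and 0.37 (Cmax) as printed, but 0.43 for both if they are swapped, which is the value in Parts B and C. With the values swapped, the limits give 68–86% (AUC) and 54–85% (Cmax) over 11 and 22 df.

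**The case against.** The best defence is that the two sentences belong together. The first rests on the planned variability and says approximately; the second then means that, at planned precision, these observed ratios keep the interval inside. Step 2 confirms the arithmetic on that reading, so this is not a calculation error. What remains is that the second sentence states its own condition, on the observed ratio only, and uses a word of certainty.

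The shortfall is also confined to the edges of the ranges. Twelve is a minimum, since 16 are enrolled; with all 16 evaluable (about 30 df) the AUC limits give roughly 95–97%. Both points are right, but the sentence is about 12.

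For Part C, a figure near one half follows by construction, because the regions were built from the half-widths. That is fair, and it shows that those regions are not independent criteria.

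A reader might infer more than the documents support:
- **That AUC coverage in Part A is as low as 54%.** The 54–60% (AUC) and 68–83% (Cmax) figures belong to a paired analysis on 11 df. The SAP's Part A model has about 22.
- **That this sentence is the only support for 12.** The precision statement and Table 5 support it too.
- **That the trial is underpowered or a decision rule fails.** Section 10.1 tests no hypothesis, Section 10.4.4 declines to set a quantitative no-go, and the sentence claims no power.

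**Conclusion.** The concern holds as a point about a stated property. Twelve completers do not make it certain that the interval lies within the regions across the printed ranges; that requires an observed within-subject SD no larger than about its planning value. On the SAP's Part A model the probability at the range limits is about 64–71% for AUC and 81–95% for Cmax, rising above 99% at an observed AUC ratio of 1.0. In Part C it is about 52–53% at the limits.

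These figures assume log-normal data, complete data on exactly 12 participants, and a true CVw equal to the protocol's value. Swapping the two Part A CVw values changes the percentages but does not make the property certain. The consequence is small: the sample-size text overstates what the design delivers, and nothing in the analysis or the interim decisions depends on it.

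**What to change.** In Sections 10.2.1 and 10.2.3, replace the claim of certainty with: *the 90% CI is expected to lie within [regions], provided the observed CVw does not exceed the planning value*. In 10.2.3, write *about the planning value*: on 11 df the half-widths at CVw 30.9% and 36.7% are 24.8% and 29.8%, slightly above the printed 24.3% and 29.2%.

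In 10.2.1, add the delivered probability with its df, for example: *with 12 completers and about 22 df, the CI lies within the regions with at least 90% probability for observed ratios of about 0.946–1.058 (AUC) and 0.467–0.535 (Cmax)*. If the two CVw values prove to be transposed, recompute these ranges.

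The cost is a few lines of text and a short calculation, and the stated ranges become somewhat narrower. N, visits and the analysis stay as they are. Section 3.1 of the current protocol describes Parts A and B as complete, so for Part A this corrects the record.
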